7. CHANGES IN THE PLANNED ANALYSIS

There are no changes to the analyses presented in the protocol.

9. APPENDICES

APPENDIX A. STANDARDS FOR VARIABLE DISPLAY IN TFLS

Continuous Variables: The precision for continuous variables will be based on the precision of the data itself. The mean, median, 25th percentile, and 75th percentile will be presented to one more significant figure than the original results; the SD will be presented to two more significant figures than the original results; the minimum and maximum will be presented to the same level of precision as the original results. P-values should be presented to 4 decimal places, unless otherwise specified.

Categorical Variables: Percentages will be presented to 1 decimal place. If the count is 0, the percentage will not be displayed. If the count equals the denominator, the percentage will be displayed as 100.

APPENDIX B. ANALYSIS VISIT WINDOWS

Assessments collected at scheduled or unscheduled visits will be mapped using the analysis visit windows listed in [Table 10](#). All diary data will be analyzed using the actual day. Refer also to Section [4.1](#).

Table 10: Analysis Windows

AVISIT	AVISITN	Range of Trial Day	Target Day	If more than one value, which value is used for analyses
Screening	1	Day -2 to 1		Last value prior to administration of study drug
Day 1	2	Day 1	Day 1	Day 1
Day 3	4	Day 2 to Day 4	Day 3	Nominal visit. If none exist, then closest to target day.
Day 5	6	Day 4 to Day 6	Day 5	Nominal visit. If none exist, then closest to target day.
Day 7	8	Day 6 to Day 8	Day 7	Nominal visit. If none exist, then closest to target day.
Day 11	12	Day 9 to Day 13	Day 11	Nominal visit. If none exist, then closest to target day.
Day 14	15	Day 12 to Day 16	Day 14	Nominal visit. If none exist, then closest to target day.
Day 21	22	Day 18 to Day 23	Day 21	Nominal visit. If none exist, then closest to target day.
Day 29	30	Day 24 to Day 34	Day 29	Nominal visit. If none exist, then closest to target day.
Day 60	31	Day 53 to Day 67	Day 60	Nominal visit. If none exist, then closest to target day.
Day 90	32	Day 76 to Day 104	Day 90	Nominal visit. If none exist, then closest to target day.
Month 6	33	Day 150 to Day 210	Day 180	Nominal visit. If none exist, then closest to target day.
Month 11	34	Day 300 to Day 360	Day 330	Nominal visit. If none exist, then closest to target day.
Month 14	35	Day 360 to Day 480	Day 420	Nominal visit. If none exist, then closest to target day.

APPENDIX C. IMPUTATION RULES FOR MISSING DATES OF PRIOR/CONCOMITANT MEDICATIONS FLAGS

For inclusion in prior and/or concomitant medication tables, incomplete medication start and stop dates will be imputed as follows:

- If it cannot be determined whether the start date of a medication is prior to the administration of study drug, it will be assumed that the medication was received prior to the administration of study drug.
- If it cannot be determined whether the stop date of a medication is after administration of study drug, it will be assumed that the medication was received after the administration of study drug.

For medications that are prohibited from randomization to Day 29, incomplete start and stop dates will be imputed as follows:

- If year is missing, day and month are missing, or the date is completely missing, no imputation will be done.
- If year and month are present and day is missing, if the month is the same as the month of randomization and/or the Day 29 visit, then assume the medication was received from randomization to Day 29. Otherwise, the prohibited medication will be assumed to not have been received from randomization to Day 29.
- If year and day are present and month is missing, then assume the medication was received from randomization to Day 29.

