5.4. Treatments and Medications

5.4.1. Prior and Concomitant Medication

A prior medication is defined as any medication that is taken within 30 days prior to dosing of study drug. A concomitant medication is defined as any medication that has a stop date that is on or after the date of study drug dosing or is ongoing after dosing.

All medications used within 30 days prior to the date of randomization up to and including Day 60 will be collected on the CRF. In addition, any concomitant medications related to AEs and any vaccinations received will be recorded for the entire length of the study (ie, through Month 14). All medications will be coded according to the World Health Organization drug dictionary (WHODrug March 2021) or higher.

The number and percentages of participants with at least one prior/concomitant medication will be summarized by treatment group. The number and percentages of all prior/concomitant medications will be summarized by treatment group, WHODrug ATC level 2 and PT. All summaries will be performed using the FAS. A listing of prior/concomitant medications by participant will be provided.

The number and percentages of participants with at least one prohibited concomitant medication (refer to ADG20-TRMT-001 Designated Background Standard of Care document) for the treatment of COVID-19 or receiving a COVID-19 vaccine will be summarized by treatment group in the FAS and the mFAS-non-Omicron. The number and percentages of these medications will also be summarized by treatment group, WHODrug ATC level 2 and PT, and a listing of prohibited medications by participant will be provided.

Medications with missing dates will follow the imputation rules in [Appendix C](#) to categorize as prior, concomitant, or prohibited up through Day 29. Medications are sorted by decreasing frequency of ATC Level 2 in the ADG20 arm, then by decreasing frequency of PT in the ADG20 arm.

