5.5.2. Supplemental Estimand Analyses

[Appendix I](#) provides an overview of the main estimation and sensitivity analyses for the supplementary estimand (Estimand 1b). Estimand 1b utilizes a hypothetical strategy for the intercurrent event of receipt of prohibited treatments (refer to ADG20-TRMT-001 Designated Background Standard of Care document) for COVID-19 (IcEV3).

For participants with IcEv3, if the participant has not had a COVID-19-related hospitalization or death prior to the intercurrent event, the primary endpoint will be set to missing. Missing data for the supplementary analysis will be carried out using an MI based strategy that includes the following three steps:

- Step 1. Missing outcomes will be imputed multiple times ($M=100$) based on the intercurrent event handling strategy
- Step 2. The logistic regression analysis model presented above will be applied to each completed data set with terms including the prognostic factors and treatment variable and estimates of the treatment effect and associated standard error will be computed.
- Step 3. The individual completed sets will be combined using Rubin's rules to produce a single inferential statement (treatment effect, standard error, and p-value) via PROC MIANALYZE.

The imputation model will be informed by the observed outcomes from participants who either did not experience the intercurrent event or met the primary endpoint prior to receiving prohibited medication. The imputation model will include the prognostic factors as listed in Section [5.5.1](#). Further variables will be considered for inclusion in the MI model on the basis they may inform missingness or be correlated with the endpoint.

The final analysis model applied to the complete data set will be the same as that for the primary analysis.

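### The partial-date rule for prohibited drugs compares calendar months instead of testing overlap with the window, so some drugs taken between randomization and Day 29 are classed as not received

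*SAP*

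**What the plan says.** SAP Appendix C has a separate set of rules for prohibited drugs: "For medications that are prohibited from randomization to Day 29, incomplete start and stop dates will be imputed as follows". There are three cases.

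- Year missing, both day and month missing, or the whole date missing: nothing is imputed.
- Only the day missing: "if the month is the same as the month of randomization and/or the Day 29 visit, then assume the medication was received" in the window. If the month matches neither, "Otherwise, the prohibited medication will be assumed to not have been received from randomization to Day 29".
- Only the month missing: "If year and day are present and month is missing, then assume the medication was received from randomization to Day 29".

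SAP 5.4.1 puts the rules to use: "Medications with missing dates will follow the imputation rules in" Appendix C, to sort drugs as prior, concomitant, or prohibited through Day 29. Two outputs depend on the result. SAP 5.4.1 tabulates by arm "The number and percentages of participants with at least one prohibited concomitant medication" for COVID-19, or a COVID-19 vaccine. In SAP 5.5.2, "Estimand 1b utilizes a hypothetical strategy for the intercurrent event of receipt of prohibited treatments" (IcEv3 in Appendix G). A participant with IcEv3 and no earlier hospitalization or death has the primary outcome set to missing and multiply imputed.

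**The concern.** Whether a drug was taken in a window depends on whether an interval, start to stop, overlaps that window. The day-missing bullet does not ask this. It takes the month of one incomplete date, compares it with two calendar months, and makes no use of the record's other date even when that date is complete. It also closes the window with the month of the Day 29 *visit*, which may take place up to five days after Study Day 29.

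A wrong *not received* drops the drug from the by-arm table. In Estimand 1b it leaves in the analysis an outcome influenced by the treatment that the estimand is meant to set aside. Nearby rules are fuller. The general prior/concomitant rule in the same appendix treats start and stop separately, and the adverse-event rule in Appendix D checks the end date and names both month and year.

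**Working it through.** The plan gives no figure to reproduce, so the check applies the bullet to dated examples and compares the answer with an overlap test: earliest possible start on or before Study Day 29, and latest possible stop on or after randomization.

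**Inputs**
- Window: randomization to Day 29 (protocol 5.6.2.1).
- Study Day = date − dosing date + 1 (SAP 4.1), so Day 29 = Day 1 + 28 days. Randomization is at the Day 1 visit (protocol 5.1). I take randomization and dosing to be on the same date.
- Day 29 visit window: +5 days, that is Day 29 to Day 34 (protocol Table 12-1).
- Drugs taken in the 30 days before dosing are recorded (protocol 5.6.1), so earlier starts are in the data.
- I require the year to match as well as the month. The bullet does not say so, but this is the reading kindest to it.

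**Case (a): partial start in the previous month, use continuing**
- Randomized 2 Dec 2021. Day 29 = 2 Dec + 28 = 30 Dec. The visit falls between 30 Dec 2021 and 4 Jan 2022.
- Record: start unknown day, Nov 2021; stop 10 Dec 2021, or ongoing.
- Appendix C: November is neither December nor January, so *not received*.
- Overlap: the start is no later than 30 Nov and the stop is 10 Dec, so the drug was certainly taken from 2 to 10 Dec. *Received*.

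**Case (b): the skipped month**
- Randomized 30 Oct 2021. Day 29 = 27 Nov. Day 33 = 1 Dec and Day 34 = 2 Dec, both inside the visit window.
- Record: unknown day, Nov 2021. Visit on 1 or 2 Dec.
- Appendix C: November is neither October nor December, so *not received*.
- Overlap: 1 to 27 Nov lies in the window, which is 27 of November's 30 days. Use in the window is likely but not proven.

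**How often case (b) is possible.** The first randomization date is not given. Assuming 1 Aug 2021, and ending at the enrollment suspension on 11 Jan 2022, there are 164 possible randomization dates. On 12 of them a late visit can skip a month. This counts calendar dates, not participants.

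**Known stop before randomization**
- Randomized 20 Nov 2021; start unknown day, Nov 2021; stop 18 Nov 2021.
- Appendix C alone: November matches, so *received*.
- SAP 5.4.1 defines a concomitant drug as "any medication that has a stop date that is on or after the date of study drug dosing or is ongoing after dosing", and Appendix G counts IcEv3 use only from administration of study drug. A stop on 18 Nov fails both.
- The text therefore points two ways, and Appendix C does not say that the complete date wins.

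**The case against.** The strongest reply is that this hardly matters.

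- Drug name and dates are minimum required data (protocol 5.6.2), and there are seven visits from Day 3 to Day 29, so partial dates should be rare.
- Exclusion 7 bars prior vaccine, monoclonal antibody and convalescent plasma, and exclusion 5 bars recent investigational treatment. Few drugs are left that could start before randomization and continue.
- COVID-19 treatment is permitted once a participant is hospitalized for COVID-19, and SAP 5.5.2 keeps the outcome when the event came first. Much in-window use therefore cannot change Estimand 1b.
- Case (b) needs a visit late in its window. For 30 October, only Day 33 or 34 will do.
- A programmer may well use the complete date anyway.

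All of this stands as a limit on size. None of it repairs the rule: no other section supplies an overlap test, and the SAP does not tell the programmer to look at the other date.

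A reader might infer more, in three ways that the documents do not support.

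- *That drugs stopped before randomization are firmly counted as received.* The definitions in SAP 5.4.1 and Appendix G imply the opposite. The defect is a missing statement of precedence.
- *That one error costs about 17% of the ADG20 arm's events.* The arithmetic is 160 × 0.12 × 0.30 = 5.8 events, and 1/5.8 = 17%. But this needs a false *received* in a participant who later had the event, which is the weaker direction. The outcome would then be imputed 100 times, not lost.
- *That year-only dates are dropped.* Appendix C says only that they are not imputed. It does not bar classification from the record's other date.

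**Conclusion.** The concern holds as a minor defect of specification. Read literally, Appendix C gives a provably wrong *not received* in case (a), and in case (b) it excludes a month that lies almost wholly in the window. It is silent on whether a known early stop overrides a month match.

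The reach is narrow: records with a partial date, in the descriptive prohibited-medication table and in IcEv3 for supplementary Estimand 1b and its control-based sensitivity analysis. Appendix H assigns the treatment policy strategy for prohibited treatments to primary Estimand 1a and key secondary Estimands 2 and 3, so those results do not change.

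The documents do not give the number of partial-date records, so no rate of affected participants can be stated. In particular, the share randomized on days 1 to 5 of a month (5/30.4 = 16%, assuming uniform entry) might be taken for one, but it is not. Case (a) also needs a prohibited drug begun in the previous month, continued past randomization, and recorded without a start day.

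**What to change.** Replace the day-missing bullet for prohibited drugs in Appendix C with:

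> Bound each partial date by its known month and year (earliest possible start, latest possible stop; ongoing = still taken), and use the complete date wherever one exists. The drug is received in the window if this interval overlaps the randomization date to Study Day 29 (not the Day 29 visit date).

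Under this text, cases (a) and (b) become *received*, and the drug stopped on 18 Nov becomes *not received*. Leave completely unknown dates as the SAP has them. Concomitant drugs are collected to Day 60, so placing every undated record in the window could flag use after Day 29 and set more observed outcomes to missing in Estimand 1b.

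The cost is a short program change, and a few records may change class. It should be settled before unblinding, when SAP 3.2 requires the SAP to be final.

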APPENDIX D. IMPUTATION RULES FOR MISSING DATES OF AES

Imputation rules for missing or partial start dates and end dates of AEs are defined below:

Missing or partial start date:

- If only Day is missing, use the first day of the month, unless:
 - The AE end date is on/after the date of study drug administration or is missing/partial AND the start month and year of the AE coincide with the start month and year of study drug administration. In this case, use the date and time of study drug administration, even if AE time was collected.
- If Day and Month are both missing, use the first day of the year, unless:
 - The AE end date is on/after the date of study drug administration or is missing/partial AND the start year of the AE coincides with the start year of study drug administration. In this case, use the date and time of study drug administration, when time is available.
- If Day, Month, and Year are all missing, the date will not be imputed. However, if the AE end date is prior to the date of administration of study drug, then the AE will be considered a pre-treatment AE. Otherwise, the AE will be considered treatment-emergent.

Missing or partial end date: Missing or partial end dates will not be imputed.

Missing start time: If the AE occurs on the date of dosing and time is missing, the AE should be assumed to be treatment emergent.

APPENDIX E. DATES OF EMERGENCE OFOMICRON VARIANT BY COUNTRY

Country	Date of First Participant With WGS-Confirmed Omicron Variant from the Same Country	Epidemiology Date of the Emergence of Omicron from the Same Country ^a
Brazil	n/a	14-Dec-21
Bulgaria	21-Dec-21	
South Africa	10-Nov-21	
Germany	25-Nov-21	
Greece	29-Dec-21	
Poland	n/a	29-Dec-21
Ukraine	5-Jan-22	
Romania	28-Dec-21	

^a Source: Date of reaching 10% Omicron of samples tested in a country.

For Brazil: Latif AA, Mullen JL, Alkuzweny M, et al. (2022a). BA.1 Lineage Report – Brazil. outbreak.info.

Retrieved 1 March 2022 from: <https://outbreak.info/situation-reports?xmin=2021-10-20&xmax=2022-01-21&loc=BRA&pango=BA.1&selected=BRA>.

For Poland: Latif AA, Mullen JL, Alkuzweny M, et al. (2022b). BA.1 Lineage Report – Poland. outbreak.info.

Retrieved 1 March 2022 from: <https://outbreak.info/situation-reports?pango=BA.1&loc=POL&selected=POL>.

APPENDIX F. RULES FOR MISSING SYMPTOM DIARY DATA

Information about COVID-19 associated symptoms is collected in a daily COVID-19 Symptom Diary as described in the protocol (Section 6.3.1.1). Participants are asked to rate the severity over the last 24 hours as *None*, *Mild*, *Moderate*, or *Severe* for the following 11 symptoms: fever, chills, cough, sore throat, congestion, shortness of breath at rest, shortness of breath with exertion, muscle or body aches, fatigue, headache, and nausea. In addition, there are two questions regarding senses of taste and smell (same as usual, less than usual, none), two questions regarding frequency of vomiting or diarrhea (none, 1-2, 3-4, ≥ 5 times), two general status questions (yes, no), and one question regarding overall severity of symptoms.

All diary data will be listed. For analysis, the answers to the questions regarding taste and smell are mapped as following: absent/none=same as usual, mild/moderate=less than usual, severe=none and the two questions regarding frequency of vomiting diarrhea are mapped as following: absent/none=none, mild=1-2 times, moderate=3-4 times, and severe= ≥ 5 times.

The following algorithms for imputing missing data (none/mild/moderate/severe) will be applied. These algorithms apply independently to individual symptom assessments.

- a. If a participant is hospitalized on or before Day 29 for a COVID-19-related hospitalization:
 - All existing data will be utilized (as the protocol indicates that the diary should be completed if feasible during hospitalization).
 - If a participant has no assessments during the hospitalization: for symptoms that were present prior to the hospitalization, the missing data are imputed as severe. If the symptom was not present at baseline or returned to absent (none) prior to the hospitalization, the symptom will be imputed as absent (none). Otherwise, if a participant has partial data available during the hospitalization: missing values are imputed as the maximum (worse) of the last observed or imputed value prior to the missing assessment and the next observed or imputed value after the missing assessment.
- b. If a participant is hospitalized on or before Day 29 for a non-COVID-19-related hospitalization, missing values during hospitalization are imputed as the maximum (worse) of the last observed or imputed value prior to the missing assessment and the next observed or imputed value after the missing assessment.
- c. If a participant discontinues from the study, is lost to follow up (LFU), or dies on or before Day 29, symptom ratings will not be imputed beyond the date of discontinuation/LFU/death.
- d. If diary data are missing when a participant is not COVID-related hospitalized and remains on study (through Day 29), data will be imputed as follows:
 - The Day 1 assessment is baseline and is performed on-site prior to study drug dosing, so the assessment is not likely to be missing. If data are present for Day 1 and is missing for a sequence of consecutive days from Day 1 but with at least one subsequent score, impute the missing values through to the first available score with the value of the first available score (provided by the participant or imputed due to hospitalization). This is a conservative assumption, so that symptom improvement or resolution is less likely to be indicated early.

- If only the Day 1 assessment is missing (for a given symptom), the value will be imputed as the Day 2 value.
- For intermittent missingness during follow-up, impute the missing values as the worse of the last available value (actually provided by the participant or imputed due to hospitalization) before the missing value and the first available value (actually provided by the participant or imputed due to hospitalization) after the missing value, irrespective of length of sequence of missing values. If the last prior and the first subsequent value are equal, then symptom improvement or resolution is based on the assumption that the situation remained stable during the missing duration. If the last prior value is worse than the first subsequent one, then symptom improvement/resolution is delayed over the missing duration until improvement/resolution is confirmed. If the last prior assessment is better than the first subsequent value, then symptom improvement/resolution is reversed earlier.

- e. If a participant has no period(s) of hospitalization and all post-Day 1 data are missing (for a given symptom) or all data, including Day1, are missing (for a given symptom), the symptom will not be imputed. If all data are missing for all symptoms, the participant will be excluded in the time-to-event analyses for improvement/resolution/sustained recovery.
- f. Missing data for the questions regarding sense of taste and smell, frequency of vomiting or diarrhea, will be imputed using the values mapped to none/mild/moderate/severe.
- g. Missing data will not be imputed for general status questions and overall severity of symptoms.

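### Symptom diary gaps right after Day 1: the back-fill rule the SAP calls conservative gives the earliest possible event date or no change, never a later one

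*SAP*

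**What the plan says.** SAP Appendix F, rule d, deals with diary data missing while the participant remains on study and is not in hospital for COVID-19. It has three bullets.

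- **Bullet 1** notes that "The Day 1 assessment is baseline and is performed on-site prior to study drug dosing". Its condition is "If data are present for Day 1 and is missing for a sequence of consecutive days from Day 1", with at least one later score. The instruction is to "impute the missing values through to the first available score with the value of the first available score". The reason given is: "This is a conservative assumption, so that symptom improvement or resolution is less likely to be indicated early".
- **Bullet 2:** "If only the Day 1 assessment is missing (for a given symptom), the value will be imputed as the Day 2 value".
- **Bullet 3:** "For intermittent missingness during follow-up, impute the missing values as the worse of the last available value" before the gap and the first available value after it, "irrespective of length of sequence of missing values". It adds that when the earlier value is the worse one, the event is held back until the end of the gap.

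Rule a (when some diary data exist during a COVID-19 hospitalization) and rule b (other hospitalizations) also use the worse of the two neighbouring values. On scope, Appendix F says: "These algorithms apply independently to individual symptom assessments". SAP Section 3.5.1 and Table 2 require all 13 symptoms to meet the criterion and to keep meeting it through Day 29.

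**The concern.** Bullet 1 ignores the Day 1 score and carries a later score backward. When symptoms have cleared by the time the diary resumes, the participant is treated as clear from Day 2. That is the opposite of the stated aim of making early events less likely.

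The bullets also leave room for two derivations. A gap between an observed Day 1 and a later score has both neighbouring values that bullet 3 needs, and Appendix F states no order of precedence. Two programmers could date the same diary differently.

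Time to sustained resolution is third among the key secondary endpoints in SAP Section 5.5.3, inside the hierarchy that controls type I error. Sustained recovery and sustained improvement use the same diary rules. At stake are the event dates, the early part of the Kaplan-Meier curves, reproducibility, and a report that would describe an earliest-date rule as conservative.

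**Working it through.** The documents give no figure that depends on this rule, so there is none to reproduce. The check is logical, then by enumeration, then by illustration.

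**1. Logic, Day 1 observed.** Let Day k be the first score after the gap.
- If Day k, or any later day, fails the criterion, the event falls after that day whatever is filled in. Back-fill has no effect.
- If Day k and all later days meet it, back-fill makes every gap day meet it. When Day 1 fails the criterion, the symptom is dated Day 2, the earliest possible. When Day 1 already meets it, back-fill and worse-of agree.

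Example for fever, Day 1 moderate, Days 2-4 missing:

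| Later scores | Bullet 1 | Worse-of |
|---|---|---|
| None from Day 5 | Day 2 | Day 5 |
| Mild on Day 5, none from Day 6 (resolution) | Day 6 | Day 6 |

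The composite date is the latest of the single-symptom dates, so the ordering carries over. The composite moves to Day 2 only if every symptom meets its criterion from Day 2, as can happen when the whole diary is blank.

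**2. Enumeration, Day 1 observed.** Four severity levels, gaps of 1-3 days from Day 2, 1-5 later scores: 16,368 patterns for each Table 2 criterion. These are pattern counts, not probabilities.

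| Criterion | Back-fill is the earliest possible date | Worse-of later than back-fill | Worse-of earlier |
|---|---|---|---|
| Resolution, 10 symptoms | 16,368 | 45 | 0 |
| Improvement, 10 symptoms | 16,368 | 387 | 0 |
| Resolution, cough/fatigue/headache | 16,368 | 372 | 0 |
| Improvement, cough/fatigue/headache | 16,368 | 372 | 0 |

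Wherever worse-of is later, it gives the latest possible date.

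**3. Enumeration, gap including Day 1.** This is the other reading of bullet 1. Days 1-2, 1-3 or 1-4 missing, 1-3 later scores, events counted from Day 2: 28,224 true courses per criterion.
- Resolution: back-fill is earlier than the truth in 972 (10 symptoms) or 3,920 (cough, fatigue, headache), and later in 0.
- Improvement of cough, fatigue and headache has the same criterion as resolution, so it is also never late.
- Improvement of the 10 symptoms: earlier in 2,922, later in 2,520, because the fill also sets the baseline. For example, fever moderate on Days 1-2 and mild from Day 3, with Days 1-4 missing, truly improves on Day 3. The filled baseline is mild, so absence is required and no event occurs.

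**4. Size, under assumptions.** The documents give no gap rate. Assume 10% of participants have a whole-diary gap from Day 2, with its end K uniform over the stated days, and a daily resolution hazard h of 0.06 or 0.09. With T = 1 + ceil(Exp(h)), P(T = 2) = 1 - e^(-h), which is 5.8% or 8.6%. A participant with a gap is dated early if 3 ≤ T ≤ K, with probability e^(-h) - e^(-h(K-1)).
- K on Days 3-5, h = 0.06: 0.942 - (0.887 + 0.835 + 0.787)/3 = 0.105, times 10% = 1.1%.
- K on Days 3-5, h = 0.09: 0.914 - (0.835 + 0.763 + 0.698)/3 = 0.148, times 10% = 1.5%.
- These events are early by 1.6 days on average. Apparent Day 2 resolution rises to 5.8 + 1.1 = 6.9% or 8.6 + 1.5 = 10.1%.
- K on Days 4-14: 3.1-4.1% are dated early, by 4.0-4.2 days on average.

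**5. Effect on the test.** Simulated age-stratified log-rank test, 160 per arm, gaps ending on Days 3-5, assuming 20% aged over 65 with 0.8 times the hazard and no adolescents. Null rejection is 5.0-5.2% under either rule and 5.0-5.1% without gaps. Power at an assumed hazard ratio of 1.4 changes by at most about 0.1 point with equal gap rates. With gap rates of 5% in one arm and 20% in the other, it moves by about 0.4-1.0 points under back-fill and 0.5-1.4 under worse-of, in opposite directions.

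**The case against.** **Bullet 1 is simply the specific rule.** Bullet 3 is worded for intermittent gaps during follow-up. Day 1 is the baseline, and the schedule of assessments starts follow-up at Day 3. If bullet 3 governed gaps right after Day 1, bullet 1 would have nothing to do. This largely stands. A reader might infer that the two bullets flatly contradict each other; the text does not support that. What is missing is a sentence on precedence. The objection does not rescue the rationale, which is wrong precisely when bullet 1 governs.

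**Bullet 1 may have been meant for gaps that include Day 1.** Its wording is awkward enough to allow this, and the overlap with bullet 3 then disappears. The rationale would still be wrong for resolution and for cough, fatigue and headache, and only mixed for improvement of the other 10 symptoms.

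**Worse-of is no more accurate.** This stands. Over all events that back-fill sets to Day 2, back-fill is 3.3-3.6 days early and worse-of 4.4-4.6 days late for gaps ending on Days 4-14. Worse-of is also more sensitive to unequal gap rates. The case for it is that it does what the SAP says it wants and matches rules a (partial data), b and d bullet 3.

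**The effect is small.** Also fair. Protocol Section 6.3.1.1 has the diary reviewed on Days 3, 5, 7, 11 and 14 and lets staff complete it by interview. The endpoint is tested only if the primary analysis succeeds.

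**Conclusion.** The rationale in bullet 1 is wrong as written. With Day 1 observed, back-fill leaves the event date unchanged or sets the earliest date the data allow, and it never delays an event. This follows from the sustained-through-Day-29 definition and needs no assumption about the data. The overlap with bullet 3 is a secondary point of clarity.

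The size is probably small and rests on assumed gap rates and hazards: roughly 1-1.5% of participants dated early if 10% have short whole-diary gaps, and 3-4% if gaps run to Days 4-14.

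A reader might infer that the rule favours ADG20 or inflates type I error. The documents do not support that. The rule is the same in both arms, the trial is blinded, no gap rates by arm are given, and the null rejection rate for short gaps stays at the nominal level. The primary endpoint and the two binary key secondary endpoints do not use the rule.

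**What to change.** Before unblinding, which is when SAP Section 3.2 requires analysis decisions to be settled:

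1. To match the stated conservative intent, fill scores missing from Day 2 up to the first available score with the worse of the Day 1 score and that first available score, whether the latter was reported by the participant or imputed because of hospitalization. State that this rule governs gaps starting on Day 2.
2. Delete or correct the sentence calling back-fill conservative.
3. Add a rule for a symptom missing on Day 1 and on one or more following days: date no event before the first available score, and state how the Table 2 baseline severity is set. Keep bullet 2 for Day 1 missing alone.
4. Report the back-fill version as a sensitivity analysis. When Day 1 fails the criterion, the two versions give the earliest and latest possible dates for that symptom.

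The cost is SAP wording, a small change in derivation code and one extra run. The downside is that worse-of lengthens symptom times and reacts more to unequal gap rates, which is why both versions should be shown.

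If the team prefers to keep back-fill as the main rule, the minimum is to state that bullet 1 overrides bullet 3, remove the conservative claim and add item 3.
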